Only a minority of heavy alcohol users develop significant liver disease. Genetic susceptibility likely contributes (Yeluru et al. 2016). The PNPLA3 gene has been reliably associated with non-alcoholic steatohepatitis and hepatitis C induced steatohepatitis (meta-analyses Chamorro et al. 2014; [name], PhD thesis). Recently, the risk (G) allele for PNPLA3 has been associated with AH, with almost double the risk for G allele carriers (Liangpunsakul et al. 2016). Existing studies characterising AH poorly identify alcohol exposure and fail to comprehensively incorporate known or suspected etiological and prognostic factors. Replication and development of this research will inform understanding of risk, treatment prognosis, and tailored behavioural treatment for AH.

AIMS

1. Examine non-inferiority or superiority of a new treatment protocol for patients with Alcoholic Hepatitis (AH) referred to the Alcohol and Drug Assessment Unit by the Department of Gastroenterology and Hepatology.
2. Replicate recent research which has found risk of AH among G allele carriers of PNPLA3.

HYPOTHESES / EXPECTED OUTCOMES

1. We expect that AH patients treated with an updated treatment protocol will have superior outcomes to historical controls of AH patients (Treatment as Usual, TAU).
 - The primary outcome will be treatment engagement and retention.
 - Secondary outcomes will include treatment initiation and drinking behaviours over treatment.
2. Genetic data will better characterize alcohol dependent patients that develop AH, compared to those that do not. The proportion of patients with risk (G) allele for PNPLA3 will be significantly higher among patients with alcoholic hepatitis than historical controls without liver disease.

PROJECT DESIGN

RESEARCH PROJECT SETTING

The research site will be based at the PAH Alcohol and Drug and Alcohol Assessment Unit (ADAU) in the Division of Medicine and Department of Gastroenterology & Hepatology (Dept. G&H).

PARTICIPANTS

RECRUITMENT

Patients are referred to the Dept. G&H for AH from the PAH Emergency Department, other medical/surgical units from other hospitals within and beyond the Metro-South District. Approximately one per week is managed for AH. All consenting patients will be offered the AH CBT program (see Procedure) and comprehensive assessment (see Measures).

ELIGIBILITY CRITERIA

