Tailored CBT Intervention: Shepard et al. (2016) demonstrate that adjunctive telephone-based therapy is a cost-effective modality with good long-term treatment outcomes. As noted, it also meets all of the requirements for a medically unwell, and frequently socially, geographically or mobility challenged AH population. Critical to AH patient abstinence is development of drinking refusal self-efficacy skills, alternative coping strategies, non-pharmacological pain management, modification of situational triggers, nutrition, psychoeducation and management of alcohol craving. The Tailored Alcoholic Hepatitis Intervention will match for the existing generic face-to-face CBT Intervention historical benchmark for length of treatment (3 months) and therapist contact (8 hours). The generic alcohol CBT program has ADAU physician consult plus 8 x 1 hour face-to-face outpatient sessions over 3 months with a clinical psychologist. The Tailored Alcoholic Hepatitis intervention will have a rapid inpatient assessment to enhance treatment engagement consisting of 2 x 20 min sessions while an inpatient, including 1) ADAU Physician assessment and 2) Clinical Psychologist treatment plan. Post discharge, the same clinical psychologist will deliver the intense 2 x weekly 20 min 'booster' telephone sessions for 3 months (totaling 8 hours). Where feasible- based on patient health and geographical location- face-to-face sessions are preferred and can be substituted for telephone sessions.

AIM 2: ASSESSING GENETIC SUSCEPTABILITY TO AH.

We will genotype PNPLA3 in AH patients via saliva sample in the current study. Saliva will be collected from patients via self-collection kit. Patient's spit approximately 2ml saliva into a funnel. Saliva is mixed with a stabilization solution making it suitable for storage. The ADAU maintains a genetically informed database of > 250 treatment seeking, alcohol dependent patients without AH, who will act as our alcohol-exposure adjusted control. Ethics approval for collection and analysis of genetic data of patients attending ADAU has previously been obtained (HREC/14/QPAH/664).

ASSESSMENT AND MEASURES

Assessments are embedded within ADAU routine protocol. They are outlined below:

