We include an additional consent provision for DNA to be available for up to 15 years and further research must be first approved by ethics committee. Patients can choose not to consent to this option. Consents will be obtained by [name] (Project manager and treating psychologist).

DATA MANAGEMENT

All data will be kept on secure, password protected, Queensland Health servers. Further access to the specific drive requires Metro South Health administration permissions and approval from the head of this department. Data will be kept consistent with ADAU (and Queensland Health) clinical guidelines, but not less than 7 years. Data used in research will be re-identifiable (coded). The coding "key" will be a password protected excel document stored within the same drive. Management practices will conform to ADAU (and Queensland Health) clinical guidelines, but not less than 7 years. Data will be destroyed via deletion of deidentified electronic file when required. Access to this deidentified data will only be granted to people approved under this application or extension to this application.

Saliva and extracted DNA samples will be stored in a locked freezer in a secure PC2 laboratory at the Queensland University of Technology (QUT). All samples will be de-identified. Laboratory protocol ensures samples are checked for viability routinely. Should a participant withdraw their consent after provision of the saliva sample their sample will be destroyed as per protocol of the PC2 laboratory at the QUT. Any electronic data generated from their sample will be deleted.

DATA ANALYSIS

Aim 1: The primary outcome will be assessed via logistic regression, where the outcome is completed treatment (0 = no, 1 = yes) and the independent variable is treatment group (0 = old protocol, 1 = new protocol). Potential confounding variables will be included as covariates (e.g. dependence severity). As the mechanism of the PNPLA3 gene is unknown it will be included as a covariate. Depending on the distribution of the number of sessions attended, parametric or non-parametric statistics may be employed to determine whether more sessions were attended on average. Again, potential confounding variables will be included as covariates.

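### The raw count of sessions attended is not comparable between an 8-session and a roughly 24-session programme, so the supporting engagement comparison favours the new protocol

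*Protocol*

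**What the plan says.** Under Hypotheses / Expected Outcomes the Protocol states: "The primary outcome will be treatment engagement and retention". Data Analysis, Aim 1, serves this in two steps. First comes a logistic regression of treatment completion (yes/no) on treatment group. Then comes a comparison of session counts, with the method to be chosen from how the counts are distributed: "parametric or non-parametric statistics may be employed to determine whether more sessions were attended on average". Potential confounders are to be covariates in both.

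The two schedules are given under Methodological Approach, Aim 1. The new programme is to match the old one's "historical benchmark for length of treatment (3 months) and therapist contact (8 hours"). The old programme: "The generic alcohol CBT program has ADAU physician consult plus 8 x 1 hour face-to-face outpatient sessions over 3 months with a clinical psychologist". The new programme has an inpatient phase "consisting of 2 x 20 min sessions while an inpatient", then after discharge "the intense 2 x weekly 20 min 'booster' telephone sessions for 3 months (totaling 8 hours"). Face-to-face sessions may be substituted for telephone sessions; their length is not given.

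The Protocol nowhere converts the session count to a share of sessions offered, to minutes or to weeks. It does not say whether the two inpatient contacts count as sessions.

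**The concern.** The design holds calendar time and therapist hours equal and lets the number of contacts differ about threefold. The analysis then compares the one quantity that was not held equal. A higher mean count under the new protocol would show mainly that its contacts are shorter and more frequent, not that patients stayed longer or took up more of what was offered. Adjusting for patient characteristics such as dependence severity cannot remove this, because the difference lies in the schedule and coincides exactly with treatment group.

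At stake is a published statement that the tailored programme improves engagement, drawn from a comparison that would often say so when retention is unchanged or worse. Controls are historical, so no randomised contrast is available to offset the artefact.

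**Working it through.** **Inputs from the Protocol.** Old: 8 sessions of 60 minutes. New: 2 contacts a week of 20 minutes for 3 months, plus 2 inpatient contacts of 20 minutes. Completion planned at 30% (old) and 40% (new), about 130 historical and 35 new patients (Sample Size section). 45% of referred patients withdraw before starting (Review and Rationale).

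**Step 1: reproduce the stated contact time.** Old: 8 × 60 min = 8 h. New, 12 weeks: 2 × 12 = 24 contacts; 24 × 20 / 60 = 8.0 h, which agrees with the Protocol. Over 13 weeks: 26 contacts, 26 × 20 / 60 = 8.67 h. With the inpatient contacts the new total is 26 to 28.

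**Step 2: ratio at equal attendance.** If both groups attend the same fraction *f*, the means are 8*f* and 24*f*, a ratio of 24/8 = 3 (26/8 = 3.25; 28/8 = 3.5).

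**Step 3: break-even.** The new mean is higher unless its attended fraction, relative to the old, falls below 8/24 = 33% (8/26 = 31%; 8/28 = 29%). For example, 50% attendance under the old protocol is 4.0 sessions; the new protocol ties at 4.0/24 = 16.7% attendance.

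**Step 4: expected means under an assumed pattern.** Assume a share attends nothing, a share attends everything, and the rest are spread evenly over 1 to S − 1 sessions (average S/2). The spread of partial attenders is an assumption, as is applying the 45% to both groups.

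- Old, 45% none, 30% all, 25% partial: 0.30 × 8 + 0.25 × 4 = 3.4.
- New, same shares: 0.30 × 24 + 0.25 × 12 = 10.2. Attended fraction 10.2/24 = 0.425, the same as 3.4/8.
- New, 20% all, 35% partial: 0.20 × 24 + 0.35 × 12 = 9.0. Attended fraction 0.375, which is worse than the old, yet the count is 2.6 times as high.
- New, 60% none, 15% all, 25% partial: 0.15 × 24 + 0.25 × 12 = 6.6. Attended fraction 0.275.

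**Step 5: chance of a significant result for the new protocol.** Simulation of 130 v 35 patients, 2,000 runs per row, two-sided 5% level, outpatient contacts only (24 v 8):

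| Never start, old / new | Complete, old / new | Welch t, raw count | Mann-Whitney, raw count | Welch t, fraction of scheduled |
|---|---|---|---|---|
| 45% / 45% | 30% / 30% | 0.96 | 0.59 | 0.02 |
| 45% / 45% | 30% / 20% | 0.91 | 0.51 | under 0.01 |
| 45% / 45% | 30% / 10% | 0.81 | 0.41 | under 0.01 |
| 45% / 60% | 30% / 15% | 0.43 | 0.05 | under 0.01 |
| 0% / 0% | 30% / 30% | 1.00 | 1.00 | 0.03 |
| 0% / 0% | 30% / 20% | 1.00 | 1.00 | under 0.01 |

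The last two rows apply if only patients who start are analysed. In the fourth row Mann-Whitney favours neither group (0.05 each way). That protection depends on excluding the inpatient contacts: if both are added for every new patient and nothing is added for old ones, Mann-Whitney favours the new protocol in about 93% of runs.

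**The case against.** The strongest reply is that this is not the main analysis. Data Analysis states that the primary outcome is assessed by logistic regression on completion, and the sample size is built on completion rates. The session comparison follows it and is worded as something that may be done. This stands: the powered test is not a session count and is not directly biased by the schedule. The count still serves the stated primary construct of engagement and retention and is placed before the secondary outcomes.

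Second, the advantage is not automatic. A reader might infer that the new protocol must win whatever its effect. The documents do not support that. The choice between parametric and non-parametric methods is left open, and with 45% withdrawing before treatment many zeros are plausible. A rank test is then less distorted, and loses its tilt in the fourth row above. If substituted face-to-face sessions run longer than 20 minutes, the gap would also narrow.

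Third, a reader might infer that completion is distorted in the same way, or that a non-parametric method cannot carry the promised covariates. Neither follows. The Protocol does not define completion by a number of sessions, and its definition may properly lie in an analysis plan that is not at hand. Rank-based and ordinal regression can include covariates.

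None of this repairs the count itself: nothing in the Protocol puts it on a common scale.

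**Conclusion.** The point holds for the supporting comparison of sessions attended, which is wrong as written. At equal attended fractions the new group's mean is about 3 times the old group's (3 to 3.5, depending on weeks and on whether inpatient contacts count). This part needs only the Protocol's own schedule, with contacts delivered as 20-minute sessions.

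The error rates rest on the assumed attendance pattern. Under equal 30% completion with 45% never starting, a false finding for the new protocol arises in about 96% (t test) or 59% (Mann-Whitney) of runs, against about 2% on the fraction scale. With completion truly worse, 20% against 30%, it arises in about 91% or 51%, against under 1%. The bias shrinks for a rank test when many more new patients attend nothing. The finding does not extend to the primary completion analysis.

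**What to change.** In Data Analysis, Aim 1, replace the number of sessions attended with one measure that means the same in both programmes. Either of these would do:

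- the share of scheduled sessions, or of the 8 scheduled contact hours, attended; or
- weeks from first to last attended outpatient contact.

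Exclude the two inpatient contacts from the measure. If face-to-face substitutes differ in length from telephone contacts, the hours version or the weeks version handles this better than a share of sessions. Name one covariate-adjusted model in advance (for example, a beta-binomial model for the share of sessions) instead of choosing the method after seeing the distribution. The raw count can still be reported descriptively beside the number scheduled.

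The cost is a change of wording and a recalculation, with no new data collection. This assumes that the clinic records, including those of the historical patients, hold attendance for each scheduled session or appointment dates (and durations, if hours are used). The Protocol does not say so, and it should be confirmed before the measure is chosen.

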Assessment of alcohol use and dependence severity include the following comprehensively validated self-report measures: Brief Michigan Alcoholism Screening Test (bMAST), Alcohol Use Disorders Identification Test (AUDIT), Timeline Follow-back Procedure (TLFB), Severity of Alcohol Dependence Questionnaire (SADQ), and the Mini Alcohol Craving Experience scale (MACE). Alcohol related psychological constructs are assessed by the Drinking Expectancy Profile (DEP; outcome expectancies and refusal self-efficacy), Motivation Thought Frequency Scale (MTF; abstinence motivation), and Dysfunctional Impulsivity Scale (DIS). Social factors are examined by the Perceived Support Scale and routine assessment of demographic information. Liver disease severity will determined by MELD score. Neurocognitive functioning are assessed by the Trails A&B. Quality of Life are assessed by the Chronic Liver Disease Questionnaire (CLDQ), Short Form-6D, Depression Anxiety,

Stress Scale (DASS-21) and General Health Questionnaire (GHQ). Blood samples are taken for full medical work up as part of routine care.

RATIONALE FOR CHOICES OF METHOD/S (TIED TO PROJECT AIMS/OBJECTIVES)

As this is foremost a service improvement and quality assurance exercise, data collected will be compared to historical controls to ensure all patients receive the best available care.

TIMEFRAMES

Based on historical trends recruitment and treatment of the required 50 AH patients will take approximately 2-years from commencement of the study. Analysis of the available data and any publication is expected to be completed within 2-years following patient intervention.

PATIENT CONSENT

In standard care each patient signs a consent form agreeing that "I understand that deidentified data (anonymous data) collected may be used for program evaluation" as well as consent to participate in the program. Consistent with recent National Statement on Ethical Conduct in Human Research updates we include an 'opt-out' option at multiple points of the program.

Regarding the updated protocol and collection of genetic material, patients are verbally informed of the protocols and purpose surrounding saliva collection and provided an information sheet and consent form specifically outlining this information (attached). Patients are provided time to read the consent form and invited to ask any questions. Patients may provide or withdraw consent at any time. Provision of consent does not alter patient care in any way.

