Analysis of secondary outcomes (drinking behaviour) will be analysed using non-parametric longitudinal mixed effects models (Multilevel Modelling). LME models are considered the gold standard in psychotherapy research as they have the advantage of modelling the trajectory of longitudinal outcomes. Missing data may therefore be imputed based on individual trajectories. See above for power analysis.

Aim 2: The primary outcome will be assessed via logistic regression, where the outcome is completed G Allele of PNPLA3 (0 = no, 1 = yes) and the independent variable is AH status (0 = control, 1 = AH). Potential confounding variables will be included as covariates (e.g. dependence severity).

ANTICIPATED RISKS AND BENEFITS

The primary concern for studies utilising historical controls is that the active condition may cause harm. Given that the active condition in this study is the addition of psychological support via enhanced personalised care, no adverse effects are expected. In contrast we expect improved therapeutic outcomes, reduced social costs, and improved patient quality of life as a result of this study.

RESULTS, OUTCOMES AND FUTURE PLANS

PLANS FOR RETURN OF RESULTS OF RESEARCH TO PARTICIPANTS

Patients will be provided the results of their psychometric assessments and blood tests as a matter of routine care. As outcomes from genetic data is not clinically meaningful the results will not be fed back to patients. Research outcomes will be made available to participants upon request; in which case a research summary will be emailed to patients upon completion.

PLANS FOR DISSEMINATION AND PUBLICATION OF PROJECT OUTCOMES

Summary statistics (e.g. descriptive and inferential statistics) of deidentified data are intended to be published within peer reviewed journals and may be presented at academic conferences. The outcomes of this study may also provide grounds for future grant applications to fund more robust clinical RCTs.

OTHER POTENTIAL USES OF THE DATA AT THE END OF THE PROJECT

Any further use of the data collected will be requested via ethics application. The most likely use is for identification of prognostic markers and intervention targets as a matter of quality assurance, program evaluation, and program development.

REFERENCES

- [name], JP, et al., 2016. Alcohol use disorders. *The Lancet* 387:988-998.

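### Of the four analyses the protocol describes, only the drinking-behaviour mixed model states no confounder adjustment, so pre-treatment differences between the cohorts may be read as a protocol effect

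*Protocol*

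**What the plan says.** The Hypotheses section expects the updated protocol to give "superior outcomes to historical controls of AH patients (Treatment as Usual, TAU"), so the controls are not randomised. On outcomes it adds: "Secondary outcomes will include treatment initiation and drinking behaviours over treatment".

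The Data Analysis section then describes four analyses:

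- **Completed treatment (Aim 1, primary), logistic regression.** Adjustment is stated, with genotype as a further covariate: "Potential confounding variables will be included as covariates (e.g. dependence severity). As the mechanism of the PNPLA3 gene is unknown it will be included as" …
- **Sessions attended (Aim 1).** Adjustment is stated a second time: "Again, potential confounding variables will be included as covariates".
- **Drinking behaviour (Aim 1, secondary).** "Analysis of secondary outcomes (drinking behaviour) will be analysed using non-parametric longitudinal mixed effects models". The text goes on to the benefit of modelling trajectories and to imputation. It names no group term, time-by-group term, baseline term or covariate.
- **PNPLA3 by AH status (Aim 2), logistic regression.** Adjustment is stated: "the independent variable is AH status (0 = control, 1 = AH). Potential confounding variables will be included as covariates".

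The Assessment and Measures section lists the TLFB, AUDIT and SADQ among the unit's routine assessments. It gives no time points.

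**The concern.** The protocol does not leave covariates to another document. It states adjustment analysis by analysis, and even repeats the statement for sessions attended. The omission for drinking therefore cannot be assumed to be covered by a general rule. Someone writing code from this text would adjust three analyses and could leave the fourth unadjusted.

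Adjustment matters at least as much for drinking as for completion. Drinking before treatment is an obvious predictor of drinking during treatment, and the protocol itself names dependence severity as a confounder for completion. The Review and Rationale section also says that about 45% of referred AH patients withdraw before starting. The new protocol is built to engage patients early, through rapid inpatient assessment. The patients who contribute on-treatment drinking data could therefore differ in severity between the cohorts because of how the programme works. A cohort difference left in the comparison could create a drinking effect or hide one.

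**Working it through.** **Textual check.** Adjustment is stated for completion, sessions and Aim 2, and not for drinking: three of the four analyses described. Treatment initiation, the other named secondary outcome, has no stated analysis at all, so it is outside this count.

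**Inputs.** The protocol gives no figure for the drinking model, so there is none to reproduce. Taken from the Sample Size section: about 130 historical and 35 new patients. The Timeframes section gives 50 new patients, so 50 was run as well. Assumed, because the protocol gives neither: a baseline cohort difference d in SD units, and a correlation ρ between pre-treatment and on-treatment drinking.

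**Formulas.** With no true effect, on-treatment drinking is y = ρx + √(1−ρ²)e, where x is pre-treatment drinking and the new cohort is shifted by d. The false group effect is:

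- follow-up compared without baseline: ρd
- change from baseline compared: (ρ−1)d
- follow-up adjusted for baseline: 0

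**Central case by hand (35 v 130, d = 0.3, ρ = 0.5).**

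- SE = √(1/35 + 1/130) = 0.190 SD.
- Follow-up bias = 0.5 × 0.3 = 0.15 SD, and 0.15/0.190 = 0.79.
- Two-sided rejection = Φ(−1.96 + 0.79) + Φ(−1.96 − 0.79) ≈ 12%.
- Change bias = (0.5 − 1) × 0.3 = −0.15 SD. The SD of change is √(2(1−0.5)) = 1, so rejection is again about 12%, with the sign reversed.

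**Simulation (3,000 runs per setting, one follow-up, linear models, two-sided 5% test, 130 v 35).** Entries are rejection rates.

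| d | ρ | Follow-up, no baseline | Change | Adjusted for baseline |
|---|---|---|---|---|
| 0 | 0.5 | 4.9% | 5.4% | 4.3% |
| 0.2 | 0.5 | 8.4% | 8.7% | 5.6% |
| 0.3 | 0.3 | 8.5% | 15.2% | 5.4% |
| 0.3 | 0.5 | 11.7% | 12.0% | 4.9% |
| 0.3 | 0.7 | 20.2% | 9.2% | 4.2% |
| 0.5 | 0.5 | 24.1% | 25.8% | 4.7% |

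At d = 0.3 the simulated biases were about +0.09, +0.15 and +0.22 SD for follow-up and −0.21, −0.15 and −0.09 SD for change, at ρ = 0.3, 0.5 and 0.7. These agree with the formulas.

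**With 50 new patients (d = 0.3, same ρ).** Follow-up rejects 7.9%, 14.0% and 23.3%; change rejects 19.4%, 15.0% and 10.6%; adjusted rejects 5.3%, 4.6% and 5.1%. A larger new cohort does not cure the problem, because the bias stays and the SE shrinks.

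The adjusted column is near 5% because the simulated cohorts differ at follow-up only through baseline. The table shows what measured baseline drinking can contribute. It says nothing about unmeasured differences.

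**The case against.** The strongest reply is that silence is not a decision. One sentence names a class of model; it does not say that the model is unadjusted. The covariate list of a secondary model is often left to the analysis plan, which is not shown, and the other three analyses make the intention to adjust fairly plain. This stands against any claim that the analysis will be unadjusted. It does not remove the inconsistency, because the protocol chose to state adjustment here and left out one comparison.

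A second reply is that a trajectory model may take pre-treatment drinking as its first time point and test group by time. A stable difference in level would then not count as an effect. That is correct for a difference that is truly stable: the change comparison would be unbiased, and the baseline-adjusted one would be off by d − ρd = (1−ρ)d. But the protocol does not state that form. Where the difference instead regresses towards the mean, the change comparison is biased by (ρ−1)d, and confounders other than baseline drinking remain uncontrolled under either form.

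Third, the rejection rates rest on assumed d and ρ and on a single follow-up rather than a full mixed model. They also suppose that all 130 historical patients have drinking data, which the protocol does not say. This stands, so the rates are illustrations and not predictions.

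A reader might also infer that the cohorts were referred by different routes, or that pre-treatment TLFB is already held for everyone. The protocol supports neither. A difference in period follows from using historical controls, but no separate historical referral route is described. Routine use of the TLFB makes baseline data likely without showing that the historical cohort has them.

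**Conclusion.** The point holds as an inconsistency that should be corrected. Of the analyses described, the drinking model alone lacks an adjustment statement, in a non-randomised comparison where drinking and dependence measures are routine. Cohort differences before treatment may then be read as a protocol effect.

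At an assumed 0.3 SD imbalance and correlations of 0.3 to 0.7, with 130 and 35 patients, a nominal 5% test rejects about 8% to 20% (follow-up without baseline) or 9% to 15% (change), against about 5% after adjustment. The two forms err in opposite directions, so the sign of the bias cannot be predicted from the protocol. With no imbalance, all three stay near 5%.

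A reader might go further and conclude that baseline differences will be counted as a protocol effect, or that this is the only group comparison lacking adjustment. The text supports neither: it does not fix the model form, and treatment initiation has no stated model at all.

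**What to change.** Add to the paragraph on secondary outcomes in the Data Analysis section:

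> The drinking models will compare the two protocols on drinking during treatment, with pre-treatment TLFB drinking as a covariate and not also as an outcome time point. They will also include dependence severity and those other pre-treatment clinical confounders of the completion model that are available in both cohorts.

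Do not require PNPLA3 in these models where historical AH controls have not been genotyped. The Aim 2 text describes genotyping the current AH patients and a genetic database of patients without AH, and shows no genotype for historical AH controls. Requiring it could lose those patients from the comparison.

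The cost is small: the wording, plus a check that the historical records hold baseline TLFB and dependence scores. If some patients lack them, the plan must say how those patients are handled.
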